Page: 1

Protocol Number: MB102134

Date: 13-Nov-2013

Observational Study Protocol MB102134

OBSERVATIONAL SINGLE-COHORT DATA BASE STUDY OF DAPAGLIFLOZIN UTILISATION IN EUROPE

This document is the confidential and proprietary information of Bristol-Myers Squibb Company, its global affiliates (BMS) and AstraZeneca (AZ). By reviewing this document, you agree to keep it confidential and to use and disclose it solely for the purpose of assessing whether your organization will participate in and/or the performance of the proposed BMS/AZ-sponsored study. Any permitted disclosures will be made only on a confidential "need to know" basis within your organization or to your independent ethics committee(s). Any other use, copying, disclosure or dissemination of this information is strictly prohibited unless expressly authorized in writing by BMS/AZ. Any supplemental information (e.g., amendments) that may be added to this document is also confidential and proprietary to BMS/AZ and must be kept in confidence in the same manner as the contents of this document. Any person who receives this document without due authorization from BMS/AZ is requested to return it to BMS/AZ or promptly destroy it. All other rights reserved.

SYNOPSIS

Observational Study Protocol MB102134

Protocol Title: Observational Single-Cohort Data Base Study of Dapagliflozin Utilisation in Europe

Department: Bristol-Myers Squibb Epidemiology and AstraZeneca Global Epidemiology

Objective(s): *Primary objective:* To describe the characteristics of European patients newly prescribed dapagliflozin by age, sex, dapagliflozin dose, country, selected co-morbidities, and selected concomitant medications.

The proposed drug utilization study will specifically describe dapagliflozin use in:

- patients > 75 years-old,
- combination use with loop diuretics or pioglitazone,
- patients with a known history of moderate or severe renal impairment and in kidney failure,
- patients lacking a diagnostic code indicating type 2 diabetes.

Study Design: This is an observational single-cohort data base study with descriptive data analyses among patients receiving dapagliflozin within electronic medical records in Europe. The study will describe the utilization pattern of dapagliflozin during the first 3.5 years after marketing authorization and launch in Europe specifically in Belgium, France, Germany, Italy, Spain and United Kingdom.

Study Population: All patients identified in the database(s) who newly received at least one dapagliflozin prescription during the study period. Dapagliflozin use will be representative of the uptake of dapagliflozin in the respective countries.

Data Collection Methods: Cegedim Strategic Data (CSD) Longitudinal Patient Databases (LPDs) come directly from physicians' EMR. Participating physicians use CSD-provided software to record their daily patient interactions and data are transmitted regularly to the Cegedim coordinating center where they are cleaned and de-identified.

Data Sources: CSD's LPDs include data from 5.8 million active patients. Over 4,000 general practitioners (GPs) in six European countries (Belgium, France, Germany, Italy, Spain and United Kingdom) are part of the LPD panels.

Patient metrics in the LPDs include Demographics (Year of birth, gender, registration dates), Medical History (Event dates, diagnosis, symptoms, risk factors, co-morbidities, referrals), Prescription (Rx dates, indication, therapeutic class, molecule, brand, dosage, posology, duration), Clinical Data (Height, weight, BP, life habits) and laboratory data.

Exposures: A patient will be identified as newly exposed when he/she has at least one dapagliflozin prescription recorded in the study database(s).

Outcomes: Outcomes include but are not limited to:

- Patient demographics: age, sex, country,
- Baseline history of type 2 diabetes,
- Baseline history of moderate or severe renal impairment,
- Concomitant medications at baseline and during dapagliflozin use.

Follow-up: Follow-up will begin on the date a patient is first prescribed dapagliflozin, which will represent the beginning of follow-up (i.e., "index date"). Follow-up will continue until the end of study or discontinuation of dapagliflozin (i.e., the final day of the days' supply for the last prescription for dapagliflozin). Follow-up will only be used to determine combination use with loop diuretics or pioglitazone. The baseline period is defined as the 12 months in the database preceding the index date.

Data Analyses: Descriptive analyses of the data will be conducted. The demographic and clinical characteristics of patients identified to have received a dapagliflozin prescription will be described at the index date. The proportion of patients receiving the drug by age group, sex, selected co-morbidities, selected concomitant medications and frequency of laboratory testing will be calculated. We will also describe dapagliflozin use within and outside the

labeled indication of type 2 diabetes. Descriptive statistics will be calculated within each database by year, and trends over time will be described. Categorical variables will be summarized by frequencies and proportions, and continuous variables will be summarized by means and standard deviations or medians and interquartile ranges.

Sample Size/Power: This is a descriptive study that will quantify new dapagliflozin use according to selected patient characteristic. Estimates of exposure, based on commercial forecasting, were performed to describe the numbers of patients that may be included in the study databases.

Estimated A	Estimated Annual Number of Dapagliflozin Users in the Cegedim Databases											
	Number of Type II Diabetics, 2010	"% of T2DM Patients Receiving OAD Treatment"	"Estimate Annual Number of OAD Users"	2012	2013	2014	2015	2016	2017	Total		
France	65000	82.7%	53755	-	269	753	1344	2957	3924	9246		
UK	85000	57.2%	48620	49	146	292	535	778	924	2723		
Italy	45000	64.5%	29025	-	261	319	435	784	929	2728		
Germany	70000	55.3%	38710	77	387	542	735	968	1161	3871		
Belgium	15000	71.9%	10785	11	86	129	183	313	388	1111		
Spain	18000	52.8%	9504	-	105	95	86	162	200	646		
	ТО	137	1254	2130	3318	5960	7526	20325				

Limitations/Strengths: Difference in the availability of data variables across the databases; misclassification of exposure and outcome; and available sample sizes (due, in part, to dapagliflozin uptake) are the major potential limitations of this study.

TABLE OF CONTENTS

TITLE PAGE	1
SYNOPSIS	2
TABLE OF CONTENTS	4
1 INTRODUCTION	6
1.1 Study Rationale	7
1.2 Research Question	7
2 OBJECTIVES	7
2.1 Primary Objectives	7
2.2 Secondary Objectives	8
2.3 Exploratory Objectives	8
3 STUDY DESIGN	8
3.1 Overview of Study Design	8
3.2 Study Population	9
3.2.1 Inclusion Criteria	10
3.2.2 Exclusion Criteria	10
3.3 Data Source/Data Collection Process	10
3.3.1 Content of the Cegedim LPDs	11
3.3.2 Content of the Cegedim LPDs for T2DM patients	12
3.4 Definitions of Study Variables	16

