1.1 Study Rationale

This drug utilization study (DUS) is being conducted as part of the BMS/AZ Dapagliflozin Risk Management Plan. Per regulatory request, this study is being conducted to describe the patients using dapagliflozin in usual clinical practice in Europe, specifically the countries reporting to our data source: Belgium, France, Germany, Italy, Spain and United Kingdom. The selection of the Cegedim Strategic Data was made because it includes data across 6 different European countries. However, an analysis of dapagliflozin patients not only required a European approval but it also requires reimbursement at the country level. As of November 2013, reimbursement was achieved in the United Kingdom and was not achieved in Belgium. In Germany, dapagliflozin was only reimbursed for 2013. Reimbursement in Italy and Spain has yet to be determined and in France, dapagliflozin is not yet reimbursed but it is expected that, should we be reimbursed, it would be only for specialist use. Since the Cegedim database includes only general practitioners, we would not expect to see any dapagliflozin users from France. Therefore, at this time, sensitivity analyses around missing data will be limited to discussions of the UK data. As this study will be on-going through 2017, country reimbursement status may change potentially resulting in more useable data from the Cegedim database.

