1.2 Research Question

Research question 1: What are the baseline characteristics of the patients prescribed dapagliflozin in Europe?

Research question 2: What proportion of patients prescribed dapagliflozin have baseline moderate to severe renal impairment?

Research question 3: What proportion of patients prescribed dapagliflozin are 75 years of age or older at the time of the index prescription?

Research question 4: What proportion of patients prescribed dapagliflozin are also users of loop diuretics or pioglitazone during the baseline period and the available follow-up period?

Research Question 5: What proportion of patients prescribed dapagliflozin does not have a diagnosis of Type II Diabetes during the baseline period or on the index date?

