3.1 Overview of Study Design

This is a cross-sectional observational single-arm cohort study with descriptive data analyses among patients receiving dapagliflozin within the Cegedim Strategic Data (CSD) Longitudinal Databases (LPDs) electronic medical records (EMRs) in Europe. The assessment of combination use with loop diuretics or pioglitazone will incorporate longitudinal follow-up (See Figure 3.1-1). The study will describe the utilization pattern of dapagliflozin during the first three and a half years after marketing authorization and launch in Europe, specifically the countries reporting to this data source: Belgium, France, Germany, Italy, Spain and United Kingdom. This analysis will be repeated at 18, 30 and 42 months from the launch of dapagliflozin (T0, estimated as January 1, 2013).

The "prescription index date" for each patient included in the study will be defined as the date a patient is first prescribed dapagliflozin.

Follow-up of Subjects

The follow-up period will be used to identify concomitant use of dapagliflozin with loop diuretics or pioglitazone. Follow-up will begin on the date a patient is prescribed dapagliflozin, which will represent the beginning of follow-up (i.e., "index date"). Follow-up will continue until the discontinuation of dapagliflozin (i.e., the final day of the days' supply for the last prescription for dapagliflozin). Once a new user of dapagliflozin discontinues his/her treatment at any time (could also include an interruption in treatment), he/she will not be identified for future analyses.

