3.3.1 Content of the Cegedim LPDs

Data are entered during usual patient care and submitted daily to the Cegedim coordinating center, cleaned and de-identified and then made available in the LPDs for research no later than one month after submission. The following anonymized patient data collected from GPs' practice will be extracted from the databases:

- Demographics (Year of birth, gender, registration dates),
- Medical History (Event dates, diagnosis, symptoms, risk factors, co-morbidities, referrals,
- Treatments (indication, molecule/brand, dosage, posology, date and length of prescription),
- Clinical Data (Height, weight, BP, life habits),
- Clinical laboratory tests, X-ray and other investigations (not available in Germany).

The median follow-up duration of a patient in the data base is 27 months in Germany, 36 months in France, 44 months in Spain, 46 months in Belgium, 112 months in Italy and 117 months in UK.

Patient data collected by Cegedim in each country participating in the LPD varies to some extent to accommodate local needs. However, all countries collect data on medical co-morbidities and outcomes, prescriptions, demographics, and physician characteristics. Key metrics of the GPs' LPDs are provided for each country in Appendix 2 (2012 data).

In the LPDs, diagnoses of clinical events are recorded as diagnostic codes (*e.g.* ICD-9, READ). These codes from the different participating countries will be harmonized based on pre-specified algorithms developed prior to the analysis and listed in the statistical analytic plan. Table 3.3.1-1 summarizes the coding conventions for each of the databases.

Table 3.3.1-1: Data Coding Conventions in the Different Countries

	Belgium	France	UK	Italy	Germany	Spain
Drug code dictionary	Association Pharmacologique Belge	Claude Bernard	Multilex	Farmadati	Abdata	Vademecum
Therapy classification	European Pharmaceutical Marketing Research Association (EphMRA)		British National Formulary (BNF)	ATC	ATC	ATC
Disease classification	Cegedim prop thesaurus (mapped	-	Read Codes	ICD-9	ICD-10	CIAP mapped to ICD-9

ATC = Anatomic, Therapeutic, Chemical

ICD = International Classification of Disease

CIAP = International Classification of Primary Care

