4.1.1 Analysis Plan for Primary Objective

Descriptive statistics will be calculated to describe baseline characteristics in dapagliflozin initiators. These characteristics include age group, sex, dapagliflozin dose, country, selected comorbidities, selected concomitant medications, frequency of laboratory testing, and available results of laboratory testing (see Table 3.4.1-1).

We will also describe dapagliflozin use within and outside (off-label use) the labeled indication of type 2 diabetes.

Categorical variables will be summarized by frequencies and proportions, and continuous variables will be summarized by means and standard deviations or medians and interquartile ranges. Because this is a descriptive drug utilization study, formal comparative tests of significance will not be performed.

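### Combination use (research question 4) is a crude proportion over unequal on-treatment follow-up, so its planned time trends can move with no change in prescribing

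*Protocol*

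**What the plan says.** Research question 4 (Protocol 1.2) asks for the proportion of dapagliflozin patients who are also "users of loop diuretics or pioglitazone during the baseline period and the available follow-up period". Baseline is fixed at the 12 months before the index date. Follow-up starts at index, and the protocol describes its end in two ways:

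- Synopsis, Follow-up: "Follow-up will continue until the end of study or discontinuation of dapagliflozin".
- Section 3.1: "Follow-up will continue until the discontinuation of dapagliflozin", with no mention of the end of study.

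The summary named in 4.1.1 is "Categorical variables will be summarized by frequencies and proportions". For research question 4 the protocol names no fixed window, person-time denominator, time-to-event summary or report of follow-up length.

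Section 3.1 repeats the analysis at 18, 30 and 42 months from launch. Under 3.1 and 3.2, patients who stop are dropped from later analyses, and earlier users still on treatment are carried forward for follow-up only. The synopsis (Data Analyses) adds: "Descriptive statistics will be calculated within each database by year, and trends over time will be described". Section 4.3 says the results go to the CHMP.

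**The concern.** For any one patient, a proportion of the ever-used kind can only stay level or rise as observation lengthens. Patients here are observed for anything from one prescription's supply to about 42 months, and the mix of lengths differs between the three analyses and between years of initiation. Follow-up length is therefore built into the reported figure. Carrying forward only those still on treatment adds to the drift, because later datasets combine new users with a group selected for long treatment.

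Combination use is a named focus of the primary objective and the sole purpose of follow-up. A reader comparing successive reports could see growing combination use, and a reader comparing initiation years within one report could see it declining. Both patterns can come from one unchanged prescribing rate. The limitations in section 5 do not mention unequal follow-up.

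**Working it through.** **The plan's own figure.** The protocol states no expected value for research question 4. The one related figure that can be reproduced is the projected number of users in Table 4.2-1: T2DM patients × share on oral treatment × yearly uptake. For the UK in 2013: 85,000 × 57.2% = 48,620, and 48,620 × 0.3% = 146, as printed. All country-year cells agree. The unrounded total is 20,325, as printed; the rounded cells sum to 20,327.

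**Inputs from the protocol.** Cuts at 18, 30 and 42 months (3.1). Forecast users of 1,254, 2,130, 3,318 and 5,960 for 2013 to 2016 (synopsis table; Table 4.2-1 prints 5,962 for 2016, which is immaterial here). These are used as relative entry numbers, spread evenly within each year.

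**Assumptions, not in the protocol.** Start rate of combination use h = 2%, 5% or 10% per year; stopping rate d = 0, 0.3 or 0.6 per year; baseline prevalence b = 10%. All are held constant, so any movement in the result is artefact.

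**Formulas.** For a patient with time a from index to the cut, the chance of new use while on treatment is

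F(a) = h/(h+d) × [1 − exp(−(h+d)a)].

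The reported total is b + (1−b) × mean of F over entry times. With even entry over T years the mean of F is

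h/(h+d) × {1 − [1 − exp(−(h+d)T)]/[(h+d)T]}.

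**Potential follow-up.** With even entry the mean at the three cuts is 9.0, 15.0 and 21.0 months. With forecast uptake:

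- 18 months: (1,254×12 + 1,065×3)/2,319 = 7.9 months, where 1,065 is half of 2,130.
- 42 months: (1,254×36 + 2,130×24 + 3,318×12 + 2,980×3)/9,682 = 15.0 months, where 2,980 is half of 5,960.
- The 30-month value is 12.0 months.

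**Across successive analyses** (h = 5%, d = 0.3 per year):

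| Measure | 18 mo | 30 mo | 42 mo |
|---|---|---|---|
| New use, even entry | 3.2% | 4.8% | 6.1% |
| New use, forecast uptake | 2.8% | 3.9% | 4.6% |
| Total with b, even entry | 12.9% | 14.3% | 15.4% |
| Total with b, forecast uptake | 12.5% | 13.5% | 14.1% |
| Total with b, even entry, protocol's datasets | 12.9% | 14.6% | 16.0% |

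The last row keeps new users plus earlier users still on treatment, as in section 3.2. The other rows keep all initiators.

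**Range.** Over all combinations of h, d, entry pattern and dataset rule, the smallest rise from 18 to 42 months is 10.9% to 11.3% (h = 2%, d = 0.6, forecast uptake, all initiators). The largest is 16.4% to 24.1% (h = 10%, d = 0, even entry).

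**By year of initiation at the 42-month cut** (h = 5%, d = 0.3, b = 10%): 18.3% for 2013, 16.4% for 2014, 13.8% for 2015 and 11.1% for the first half of 2016. The artefact here is a fall.

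**With a fixed window.** New use within 12 months of index, censored at stopping or data cut, gives a total of b + (1−b)(1 − exp(−h)) = 10% + 90% × 4.88% = 14.4% at h = 5% (11.8% at 2%, 18.6% at 10%). It is the same at every analysis and for every entry year with enough follow-up to estimate it.

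**The case against.** **The study is descriptive.** Section 4.1.1 excludes formal comparative tests. That is true, but the trend description is itself planned output, and it is what the artefact distorts.

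**The SAP may settle it.** Windows and denominators are often SAP matters, and the SAP has not been seen. It could report them. However, section 4.1 says the SAP elaborates the protocol's plans and that major modifications need an amendment, and the measure "during the baseline period and the available follow-up period" is the protocol's own.

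**By year could mean calendar year of use.** Each window would then be at most 12 months, and accumulation to 42 months would not arise in those tables. This reading limits the by-year part. It does not touch the repeated analyses at 18, 30 and 42 months.

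**Part of the measure is sound.** The 12-month baseline is fixed, and Table 3.4.1-1 already lists concomitant medication before, at initiation of and during use. Baseline and at-index use do not depend on follow-up.

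**Country comparisons.** A reader might infer that planned comparisons between countries are distorted too, pointing to "In Germany, dapagliflozin was only reimbursed for 2013" and "The median follow-up duration of a patient in the data base is 27 months in Germany" (against 117 months in the UK). The protocol does not support this. Country is a descriptive stratum, results are given within each database, and no cross-country comparison for research question 4 is stated. The 27 and 117 months are time in the database, not time on dapagliflozin.

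**A more than twofold rise.** With h = 5%, no stopping and even entry, new use goes from 3.7% to 8.3%. That covers new use only, leaves out the baseline part of research question 4, and sets aside the protocol's rising uptake.

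**Conclusion.** The point holds for time trends. As written, the follow-up part of research question 4 rises across the 18-, 30- and 42-month analyses at an unchanged co-prescribing rate and, at a single cut, looks lower for more recent initiators.

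The size depends on rates the protocol does not give. Under the central assumptions and forecast uptake, the drift from 18 to 42 months is 1.8 percentage points in new use (2.8% to 4.6%) and 1.6 points in the total with 10% baseline use (12.5% to 14.1%). It is under half a point if starts are rare and stopping is fast, and nearly 8 points (16.4% to 24.1%) if starts are frequent and nobody stops. The conclusion does not extend to baseline use, at-index use or a planned country comparison. The change should be made, because trends in a regulator-requested measure should not depend on length of observation.

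**What to change.** In research question 4 and section 4.1.1:

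1. Report baseline use and use at the index date separately from new use during treatment.
2. Give new use as cumulative incidence within a fixed window from index, for example 6 and 12 months, censored at discontinuation, loss from the database or data cut. Add events per 100 person-years on dapagliflozin.
3. Put median on-treatment follow-up beside each figure.
4. Base statements about trends over time on these measures.
5. Reconcile the synopsis and section 3.1 on when follow-up ends.

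The cost is a wording change and a few more tables, from prescription dates and durations already held in the databases. The downside is that fixed-window figures use less of the late follow-up; the person-time rate still uses it.

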1 INTRODUCTION

Dapagliflozin (BMS-512148) is a highly potent, selective, and reversible inhibitor of the human renal sodium glucose co-transporter (SGLT2), the major transporter responsible for renal glucose reabsorption. Dapagliflozin lowers plasma glucose by inhibiting the renal reabsorption of glucose, and by promoting its urinary excretion making it a member of an emerging therapeutic class in the treatment of type 2 diabetes mellitus (T2DM).

Dapagliflozin is indicated in adults aged 18 years and older with type 2 diabetes mellitus (T2DM) to improve glycaemic control as:

- Monotherapy when diet and exercise alone do not provide adequate glycaemic control in patients for whom metformin is considered inappropriate due to intolerance.
- Add-on combination therapy in combination with other glucose lowering medicinal products including insulin, when these, together with diet and exercise, do not provide adequate glycaemic control.

According to the summary of product characteristics (SmPC), the recommended posology and method of administration are the following:

- The recommended dose is 10 mg dapagliflozin once daily for monotherapy and add-on combination therapy with other glucose lowering medications including insulin. When dapagliflozin is used in combination with insulin or an insulin secretagogue, such as a sulphonylurea, a lower dose of insulin or insulin secretagogue may be considered to reduce the risk of hypoglycaemia.
- Dapagliflozin can be taken orally once daily at any time of day with or without food. Tablets are to be swallowed whole.

The following precautions for use must be taken for the following special populations:

- Renal impairment: The efficacy of dapagliflozin is dependent on renal function, and efficacy is reduced in patients who have moderate renal impairment and likely absent in patients with severe renal impairment. Dapagliflozin is not recommended for use in patients with moderate to severe renal impairment (patients with creatinine clearance [CrCl] < 60 ml/min or estimated glomerular filtration rate [eGFR] < 60 ml/min/1.73 m²). No dosage adjustment is indicated in patients with mild renal impairment.
- Hepatic impairment: No dosage adjustment is necessary for patients with mild or moderate hepatic impairment. In patients with severe hepatic impairment, a starting dose of 5 mg is recommended. If well tolerated, the dose may be increased to 10 mg.
- Elderly (≥ 65 years): In general, no dosage adjustment is recommended based on age. Renal function and risk of volume depletion should be taken into account. Due to the limited therapeutic experience in patients 75 years and older, initiation of dapagliflozin therapy is not recommended.
- Patients at risk for hypotension due to effect of dapagliflozin on diuresis and blood pressure: Caution should be exercised in patients for whom a dapagliflozin-induced drop in blood pressure could pose a risk, such as patients with known cardiovascular disease, patients on anti-hypertensive therapy with a history of hypotension or elderly patients. For patients receiving dapagliflozin, in case of intercurrent conditions that may lead to volume depletion,

careful monitoring of volume status (e.g. physical examination, blood pressure measurements, and laboratory tests including haematocrit) and electrolytes is recommended. Temporary interruption of treatment with dapagliflozin is recommended for patients who develop volume depletion until the depletion is corrected.

